1.5. Sample Size

The planned sample size for this study is 1050 randomized and treated subjects. These subjects will be allocated into 3 treatment groups in a 1:1:1 ratio. Pair-wise testing of each ALD403 group vs. placebo will be performed. Three hundred and fifty subjects per group provides at least 90% power for the primary endpoint for each comparison assuming a treatment effect of at least 1 day and a common standard deviation of 4 days or less. For the key secondary 75% responder rate endpoints 90% power is achieved for the pair-wise comparisons, assuming a placebo responder rate of 20%, and an ALD403 rate of 31%. These sample size calculations have been performed using Pass 2008 and are based upon a t-test and chi-squared test that should approximate the ANCOVA and CMH tests.³

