2.5. Statistical Assessment of the Trial Objectives

2.5.1. Primary Endpoint

Hypothesis testing will be performed for the primary endpoint: change in frequency of migraine days (Weeks 1-12). This endpoint will be calculated as outlined in Section 2.2.2 and will utilize the missing data rules provided in Section 2.7.2. Summary statistics including confidence intervals for the treatment differences will be used to summarize the results for the primary endpoint. Testing will also be employed. The hypotheses tested are

$$H_0: \Delta_{\text{plb}} = \Delta_{403} \qquad H_a: \Delta_{\text{plb}} \neq \Delta_{403}$$

where Δ_{403} is the change in migraine days for subjects in the ALD403 treatment arm and Δ_{plb} is similarly defined for the placebo subjects. The change from baseline is expected to be negative as migraines are being reduced. While the test outlined above is two sided, as is the alpha level used for this study (i.e. 5%), clinically relevant results require a larger reduction of migraines on the ALD403 arms.

An ANCOVA model will be used to test for a difference between treatment arms. This model will include the change from baseline measure as the response variable. Treatment and variables measuring the stratification factors concepts: baseline migraine days (continuous covariate) and prophylactic medication use (binary covariate: use vs. no use) will be the independent variables.

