2.7.3. Sensitivity Analyses

A number of sensitivity analyses will be performed. The first group of sensitivity analyses will look at the missing data rules as outlined below.

1. The primary endpoint will be analyzed using a modification to Missing Date Rule 2 to better understand the robustness of the selected algorithm. The analysis replaces X_p with X_b , where X_b are the baseline average daily results, if the subject withdrew from the study due to an adverse event, study burden, lack of efficacy or worsening of study indication or if the subject died.
2. The primary endpoint will be analyzed using repeated measures where the individual time periods (Weeks 1-4, 5-8 and 9-12) are included in the model and Missing Date Rule 2 is not used. Hence, subject who do not complete the diary for more than 7 days out of 28 are not included for that 4 week period. The model will specify an unstructured variance/covariance matrix and include the treatment group, timepoint, baseline, and treatment group-by-timepoint interaction. The Kenward-Roger approximation will be used to estimate the degrees of freedom.

The second group of sensitivity analyses change the definition of baseline. Baseline will be redefined using 28-days of headache diary data ending on the day of the first dose. The primary analysis will be repeated using this updated definition of the baseline.

Finally, a repeated measures model will be run that includes all 6 four week intervals and both missing data rules outlined in Section 2.7.2. This model will be identical in structure to the model specified for the missing data sensitivity analysis outlined above but will look at how the primary analysis, based upon the ANCOVA model, compares to a repeated measures analysis.

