3.4. Analysis of Efficacy Endpoints

3.4.1. Migraine/Headache Days

Summary tables for the number of migraine/headache days, change from baseline and the percent change by 4, 12 and 24 week intervals and treatment group will be produced. The treatment difference and associated confidence interval will also be provided. These confidence intervals will be based on normal approximation. Stratification will not be used for these intervals.

The SAS procedure, Proc Mixed will be used to generate the ANCOVA model outlined in Section 2.5.

Plots of the migraine days, and change from baseline will be produced. These plots will use the four week intervals as the X-axis. A separate set of graphs that provide histograms of the Week 1 to 12 results for these three parameters will also be produced. A plot for the cumulative distribution function of change from baseline migraine days for Weeks 1-12 will be produced.

The change in frequency of migraine days for Weeks 1-12 will be summarized within the subgroups outlined in Section 2.7.1. A forest plot of the treatment difference and associated confidence interval will also be presented.

Sensitivity Analyses

Summary statistics for the sensitivity analyses as outlined in Section 2.7.3 will be produced. These summary statistics will include the primary endpoint with the modified Missing Data Rule #2, with the different baseline definition and for the sensitivity repeated measures models. For the repeated measures the estimated treatment difference, for each time point, and associated confidence interval will be estimated using SAS procedure, Proc Mixed. The overall Week 1-12 estimated treatment difference, associated confidence interval and p-value will be reported.

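### Both repeated-measures sensitivity models leave out prophylactic medication use, and the six-interval one nearly reproduces the primary ANCOVA by construction

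*SAP*

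**What the plan says.** SAP 2.5.1 defines the primary model as an ANCOVA on the Weeks 1-12 change. Besides treatment, continuous baseline migraine days and "prophylactic medication use (binary covariate: use vs. no use) will be the independent variables". SAP 1.3 makes prophylactic use one of the two stratification factors.

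SAP 2.7.3 has two repeated-measures analyses of migraine days. Analysis 2 uses the three intervals of Weeks 1-12 without Missing Data Rule 2. Its model is to "include the treatment group, timepoint, baseline, and treatment group-by-timepoint interaction", with unstructured covariance. The last analysis "includes all 6 four week intervals and both missing data rules outlined in Section 2.7.2" and takes the same model structure. Its stated purpose is to compare the ANCOVA with a repeated-measures analysis. SAP 3.4.1 adds, for the repeated-measures models: "The overall Week 1-12 estimated treatment difference, associated confidence interval and p-value will be reported".

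Neither model lists prophylactic use. SAP 2.7.3 gives no reason, and SAP Section 4 does not mention it.

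**The concern.** A sensitivity analysis is easiest to read when it changes one thing. Analysis 2 changes two: the handling of sparse intervals and the covariate set. A gap from the primary result cannot then be assigned cleanly to missing data, and the standard error carries variation that the primary model removes.

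The last model has a different limit. It uses the same completed data as the primary analysis and reports the same Week 1-12 contrast, so close agreement is close to guaranteed. It sits under the sensitivity-analysis heading with an estimate, confidence interval and p-value. Without a label, a reader of the study report could take that agreement as reassurance about missing diary data, on which this model carries no information.

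**Working it through.** **1. The plan's own figures.** SAP 1.5 claims 90% power or more on the primary endpoint with 350 in each arm, "assuming a treatment effect of at least 1 day and a common standard deviation of 4 days or less". The standard error is 4 × √(2/350) = 0.302, 1/0.302 = 3.307, and Φ(3.307 − 1.960) = 0.911. For responder rates of 20% and 31% the power is 0.918. Both claims reproduce. The point concerns model structure and does not depend on them.

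**2. No interval is missing in the last model.** Under SAP 2.7.2, Rule 1 rescales intervals with at least 21 diary days. Rule 2 covers the rest as 28(W·Xc + (1 − W)·Xp). With no diary days W = 0, and the result is 28·Xp, the previous imputed rate. Protocol 8.1 requires at least 24 of 28 diary days before randomisation, so taking baseline as the interval before Weeks 1-4, a starting value always exists.

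**3. Why the contrast repeats.** Write ΔY for the difference in mean Weeks 1-12 change between two arms and ΔX for the difference in mean baseline. Leave prophylactic use aside for the moment.
- ANCOVA on the average: ΔY − b₁·ΔX, where b₁ is the pooled within-arm slope of the Weeks 1-12 average.
- Unstructured model on complete data with treatment-by-timepoint and one baseline term: ΔY − b₂·ΔX, where b₂ is a single slope estimated from all six intervals.
- Difference: (b₁ − b₂)·ΔX. It vanishes if each interval has its own slope.

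So two features separate the last model from the primary: the shared slope and the omitted covariate. Neither concerns missing data.

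**4. Size of the omitted covariate.** Assumptions not in the documents: 45% prophylactic users, and an effect d of prophylactic use on the change score.
- Shift: d × imbalance between arms. With d = 0.8 and simple randomisation, the standard deviation of the imbalance is √(2 × 0.45 × 0.55/350) = 0.0376. The mean absolute shift is 0.798 × 0.0376 × 0.8 = 0.024 day (95th percentile 1.96 × 0.0376 × 0.8 = 0.059).
- The trial uses stratified permuted blocks. Simulated with assumed block sizes of 3, 6 or 12, the mean shift is 0.001 to 0.002 day (95th percentile 0.003 to 0.006).
- Standard error: the ratio is √(1 + 0.2475·d²/σ²). The simulated primary standard error of 0.265 gives σ = 0.265/√(2/350) = 3.51 and σ² = 12.3. For d = 0.8 the ratio is √(1 + 0.158/12.3) = 1.006. For d = 2 it is √(1 + 0.990/12.3) = 1.039 (simulated 1.038).

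**5. Simulation of the model as written.** 1,050 subjects, three arms, stratified blocks, six intervals of 28 daily records, Rules 1 and 2 applied, 150 trials × 2 contrasts per scenario. Further assumptions: baseline mean 16 and SD 4.5; within-subject correlation 0.7; 7% sporadic missing days plus 12% dropout over 24 weeks; prophylactic effect 0, 1 or 2 days; baseline slope constant at −0.4, or drifting from −0.25 to −0.55 or from −0.10 to −0.60.

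| Source of difference from the primary ANCOVA | Root-mean-square shift, days (largest) | Standard error relative to primary |
|---|---|---|
| Omitting prophylactic use alone | 0.0006 to 0.0054 (0.019) | 0 to +3.8% |
| Shared slope alone, true slope constant | 0.0014 to 0.0017 | −0.1% to +1.0% (both slope rows) |
| Shared slope alone, true slope drifting | 0.014 to 0.024 (0.088) | as above |
| Last model as written | 0.002 to 0.024 (0.089) | 1.00 to 1.047 |

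The correlation of the last model's estimate with the primary estimate was 0.996 to 1.000.

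**6. After alignment.** Adding prophylactic use alone leaves the shared-slope difference. Adding both prophylactic-use-by-timepoint and baseline-by-timepoint makes estimate and standard error equal the primary ANCOVA to below 1e-13.

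**The case against.** The strongest reply is that the SAP does not offer the last model as a missing-data check. It separates that model from the group addressing the missing data rules and describes it as a comparison of methods, for which holding the completed data fixed is the ordinary choice. Analysis 1 substitutes baseline rates after specified withdrawals, and analysis 2 drops Rule 2 for Weeks 1-12. SAP 2.3 also makes p-values outside the testing sequence exploratory. All of this stands. A reader might infer that the SAP presents the last model as proof of robustness to missing data; its text does not say so. What is lacking is a sentence ruling that reading out.

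A second reply is that dropping a stratification factor is numerically trivial. For the point estimate this is right. A reader might infer a shift of about 0.02 day, but that size belongs to simple randomisation, not to the stratified blocks in SAP 1.3. The wider standard error and the mixed comparison in analysis 2 remain, though both are small.

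A third reply is that aligning the covariates makes the last model more redundant, as step 6 shows. That is true, and it is why the label is needed as well as the covariate.

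**Conclusion.** The point holds as a minor improvement. Prophylactic medication use should be in both repeated-measures models. Leaving it out moves the estimate by about 0.002 day on average for an assumed 0.8-day effect and widens the standard error by about 0.6% to 4% for assumed effects of 0.8 to 2 days. The six-interval model nearly duplicates the primary contrast, and its agreement says nothing about missing data.

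A reader might go further and conclude that the omitted covariate is the only thing that can move the last model. The listed terms do not support that: one baseline slope is shared over six intervals, so Weeks 13-24 enter the baseline adjustment of the Week 1-12 contrast. If the slope drifts, this is the larger source.

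The sizes rest on assumed prophylactic effects, share of users, slopes and missingness, since the documents give none. They also take the covariate to be the as-randomised stratum. Errors in stratum assignment would move the shifts towards the simple-randomisation bound (0.008 to 0.072 day for the omission alone). No confirmatory conclusion changes.

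**What to change.** In SAP 2.7.3:

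- Add prophylactic medication use, and preferably baseline-by-timepoint, to the model statement for analysis 2 and for the six-interval analysis. Analysis 2 then differs from the primary analysis mainly in how sparse intervals are handled.
- State that the fully imputed six-interval model compares model forms and is not evidence of robustness to missing data, which analyses 1 and 2 address.

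Running the six-interval model with Rule 1 only is optional, because analysis 2 already does this for Weeks 1-12. If the paragraph is edited, it could also say at which data cut the six-interval model is run. SAP 1.4 places the primary analysis at the last subject's Week 12 visit, when later intervals are incomplete.

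The cost is SAP wording and two model statements. The covariate is already collected and no new data are needed.

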2.7.4. Interim Analyses and Data Monitoring

A Data Monitoring Committee (DMC) will periodically review safety data during the enrollment and treatment phases of this study at regularly scheduled meetings as specified in the DMC Charter. The DMC will advise the Sponsor regarding the continuing safety of trial subjects and those yet to be recruited to the trial, as well as the continuing validity and scientific merit of the trial. The DMC is not charged with stopping the trial early for efficacy.

2.7.5. Multicenter Studies

Data from all sites will be pooled for presentation.

2.7.6. Pooling Strategy for Strata

No pooling will be done.

3. STATISTICAL SUMMARIES

3.1. General Conventions

Unless otherwise stated, summary statistics including the number of subjects (n), mean, standard deviation, median, minimum and maximum will be presented for continuous variables.

Generally, the minimum and maximum values will be presented to the same decimal precision as the raw values, the mean and median values to one more, and the standard deviation, to two more decimal places than the raw values. This decimal place convention may be followed for all data elements. For categorical variables, per category, the absolute counts (n) and percentages (%) of subjects with data, and if appropriate, the number of subjects with missing data, will be presented. Percentages will be presented to one decimal place.

For AEs, medical history and concomitant medications reported on a per-subject basis, the denominator for the percentage calculation will be the number of subjects at risk in each treatment group. A subject will be considered at risk if the subject is in the analysis set and in the subgroup of interest.

All p-values will be rounded to 4 decimal places. If a p-value is less than 0.0001 it will be displayed as “< 0.0001”.

Unless otherwise specified all summaries will be performed by treatment group, all efficacy analyses will be based upon the full analysis population, all safety as well as demographic and baseline characteristic analyses will be based upon the safety population and all PK analyses will be based upon the PK population.

3.2. Definition of Baseline

Baseline assessment for migraine and headache endpoints will be based upon the data recorded in the headache eDiary during the 28 days following screening. For other variables, the baseline assessment will be the latest available valid measurement taken prior to the administration of Investigational Product. This will generally be Day 0.

3.3. Clinical Trial Subjects

3.3.1. Subject Disposition

The number of subjects randomized, treated, discontinued Investigational Product early, and terminated from the clinical trial early will be summarized. The reason for early discontinuation of Investigational Product or termination from the clinical trial will be summarized. Additionally, the summary of subjects present at each visit will be summarized. Subjects randomized but not included in the full analysis population and the reasons for exclusion will be summarized. The number of subjects screened and summary of screen failure reasons will also be summarized.

A listing of entry criteria that were not met will be produced.

3.3.2. Analysis Population

The number of subjects in each analysis population will be summarized.

3.3.3. Demographics and Baseline Characteristics

Demographic and baseline characteristics will be summarized descriptively by treatment group.

3.3.4. Prior and Concomitant Medications

Medications with a stop date before the study treatment dosing date will be considered prior medications. Medications with a start or stop date on or after the treatment dosing date will be considered concomitant medications. All medications marked as ongoing are concomitant medications.

A medication with an incomplete stop date will be considered concomitant if:

- Month is missing and year is equal to or after the year of treatment dosing date
- Day is missing and year is equal to the year of the treatment dosing date and month is equal to or after the month of the treatment dosing date.

Concomitant medications will be summarized by treatment group. All medications will be provided in a listing.

The headache medications recorded in the eDiary will not be integrated with the concomitant medications as these two data capture tools have distinctly different format, purpose and functionality. These diary-based results will be summarized in a separate series of outputs. For these the percent of days that subjects used headache medication within each 4 week interval and in the trial as a whole will be summarized by treatment group. These summary measures will only include subjects who have completed the eDiary at least 21 days of the 28 days for the selected interval. In addition to the overall summary, descriptive statistics will be provided for each type of medication: Ergotamine, Triptan, Analgesic, Opioid and Combination Analgesic.

3.3.5. Medical History

Medical History will be tabulated by system organ class, preferred terms and treatment groups.

Migraine History including age at diagnosis, the average number of headache days, migraine days, and migraine attacks per 28 day period in the 3 months prior to screening, suffers from aura, medication overuse headache diagnosis, length of chronic migraine history, as well as the timing of the start of migraines in relation to puberty/ menarche and hormone migraine history for females will be summarized in a table by treatment groups.

3.3.6. Clinical Trial Treatment

Total volume infused, number of infusions and reason for dose interruption will be listed as well as summarized in a table.

3.3.7. eDiary Compliance

The rate of missing eDiary data within each four week interval, which is defined as $(\text{number of days with missing eDiary data} / 28) * 100$, will be summarized descriptively. A day will be considered as missing if the subject did not interact with their eDiary and the subject did not experience a headache on that day.

3.4. Analysis of Efficacy Endpoints

3.4.1. Migraine/Headache Days

Summary tables for the number of migraine/headache days, change from baseline and the percent change by 4, 12 and 24 week intervals and treatment group will be produced. The treatment difference and associated confidence interval will also be provided. These confidence intervals will be based on normal approximation. Stratification will not be used for these intervals.

The SAS procedure, Proc Mixed will be used to generate the ANCOVA model outlined in Section 2.5.

Plots of the migraine days, and change from baseline will be produced. These plots will use the four week intervals as the X-axis. A separate set of graphs that provide histograms of the Week 1 to 12 results for these three parameters will also be produced. A plot for the cumulative distribution function of change from baseline migraine days for Weeks 1-12 will be produced.

The change in frequency of migraine days for Weeks 1-12 will be summarized within the subgroups outlined in Section 2.7.1. A forest plot of the treatment difference and associated confidence interval will also be presented.

Sensitivity Analyses

Summary statistics for the sensitivity analyses as outlined in Section 2.7.3 will be produced. These summary statistics will include the primary endpoint with the modified Missing Data Rule #2, with the different baseline definition and for the sensitivity repeated measures models. For the repeated measures the estimated treatment difference, for each time point, and associated confidence interval will be estimated using SAS procedure, Proc Mixed. The overall Week 1-12 estimated treatment difference, associated confidence interval and p-value will be reported.

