3.4.2. Responder Rates

The 50%, 75% and 100% responder rates will be determined as outlined in the missing data Section 2.7.2 and the endpoint definition in Section 2.2.2. The number of subjects who are responders and the rate (full analysis population as the denominator) will be summarized for each treatment group at each 4, 12, and 24 week interval. The difference in rates and associated confidence interval will also be produced. These confidence intervals will be calculated based upon the normal approximation for two independent proportions. Stratification will not be used for these intervals. The SAS procedure, Proc Freq, will be used to calculate these confidence intervals. Any interval for which the normality assumption is questionable (i.e. $np < 5$ or $nq < 5$) will be flagged.

Plots of the percent of responders across time, for each response level, will be produced. These plots will use the four week responder rates.

A p-value for the difference in rates for the key secondary endpoints will be based upon the CMH test outlined in Section 2.5.

Should the as randomized and ‘true’ values for the stratification factors differ, the as randomized values will be used within these CMH tests. The SAS procedure, Proc Freq, will be used to calculate this p-value. Cumulative distribution of the responder rate will be plotted.

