3.4.2.4. Acute Migraine Medication Days

Similar outputs will be produced for the Acute Migraine Medications Days as were produced for the primary endpoint. These will include 4 week, 12 week and 24 week summary measures and the p-value from the test outlined in Section 2.5.

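### The primary p-value comes from ANCOVA, but the only confidence interval specified for the primary difference is unadjusted; the ANCOVA LS-mean difference and its interval should be the reported estimate

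*SAP*

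**What the plan says.** SAP 2.5.1 defines the confirmatory test: "An ANCOVA model will be used to test for a difference between treatment arms". The response is change from baseline; the terms are treatment, baseline migraine days as a continuous covariate, and prophylactic medication use as a binary one. The same section, like Protocol 13.4.2, promises confidence intervals for the treatment differences but does not say how they are computed.

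The method appears only in SAP 3.4.1, with the summary tables: "These confidence intervals will be based on normal approximation. Stratification will not be used for these intervals". The next paragraph names Proc Mixed as the procedure for the ANCOVA and lists no output from it. Neither document mentions an LS mean, an adjusted difference or an ANCOVA-based interval.

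A model-based difference is specified elsewhere, for the repeated-measures sensitivity models. Section 2.7.3 describes the model: "The model will specify an unstructured variance/covariance matrix and include the treatment group, timepoint, baseline, and treatment group-by-timepoint interaction". Section 3.4.1 adds, under its sensitivity analyses: "The overall Week 1-12 estimated treatment difference, associated confidence interval and p-value will be reported".

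Section 3.4.2.4 carries the primary-endpoint outputs over to a key secondary endpoint: "Similar outputs will be produced for the Acute Migraine Medications Days as were produced for the primary endpoint". It describes them as summary measures plus the p-value from the test. For responder rates, section 3.4.2 has a parallel rule: "These confidence intervals will be calculated based upon the normal approximation for two independent proportions. Stratification will not be used for these intervals".

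**The concern.** An estimate, its interval and its p-value should come from one analysis. Here the p-value adjusts for baseline and prophylactic use, while the specified interval uses neither. This has three consequences.

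- The raw interval carries outcome variance that the baseline covariate would remove, so it is wider than it needs to be.
- The raw point estimate is not corrected for whatever baseline imbalance remains after stratified randomisation.
- The interval can include zero when the p-value is below 0.05, or exclude zero when it is not.

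The SAP asks for a matched estimate, interval and p-value for the sensitivity models but not for the primary analysis. If the ANCOVA interval were promoted to the headline after unblinding, that would be a post hoc choice, because the raw one is what is prespecified.

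What is at stake is the precision and coherence of the reported primary effect. The gatekeeping in SAP 2.3 runs on p-values alone.

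**Working it through.** **Inputs.** Two-sided 5% level (SAP 2.5.1). From SAP 1.5: 1050 subjects in three equal groups, so 350 per arm; planning difference 1 day; SD 4 days; 75% responder rates 20% and 31%. The correlation r between baseline migraine days and change is not in the documents. I take 0 to 0.5 as an assumed range.

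**The plan's own figure.** The standard error of a raw difference is 4 × √(2/350) = 0.302 days. Power for 1 day is Φ(1/0.302 − 1.96) = 91.1% by normal approximation, and 91.0% by the noncentral t with 698 degrees of freedom. The stated power of at least 90% reproduces.

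**Interval width.** Raw half-width: 1.96 × 4 × √(2/350) = 0.593 days. The ANCOVA residual SD is 4 × √(1 − r²), so the ANCOVA half-width is 0.593 × √(1 − r²), and the raw interval is wider by the factor 1/√(1 − r²).

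**Agreement with the p-value.** This was simulated with 10,000 trials per cell, two arms of about 350, and assignment balanced within the four strata (<17 or ≥17 migraine days, by prophylactic use). The last two columns are for a true effect of 1 day.

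| r (assumed) | ANCOVA half-width, days | Raw interval wider by | Raw interval coverage | ANCOVA significant, raw interval includes 0 | Raw interval excludes 0, ANCOVA not significant |
|---|---|---|---|---|---|
| 0.2 | 0.581 | 2% | 95.1% | 0.95% | 0.45% |
| 0.3 | 0.565 | 5% | 95.7% | 1.90% | 0.37% |
| 0.4 | 0.543 | 9% | 95.9% | 2.68% | 0.30% |
| 0.5 | 0.513 | 15% | 96.8% | 3.68% | 0.19% |

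At r = 0 the half-widths are equal, raw coverage is 95.1%, and the two analyses disagree in 0.2% to 0.5% of trials. ANCOVA coverage is 94.8% to 95.0% for r of 0.2 to 0.5.

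Over the same r of 0.2 to 0.5, a true effect of 0.5 day gives 2.3% to 12.1% ANCOVA-only and 1.3% to 1.6% interval-only. With no effect the figures are 0.8% to 2.4% and 0.4% to 0.6%.

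The stratified design matters. A large-sample calculation without stratified assignment gives 1.9% to 6.2% ANCOVA-only at 1 day. This trial stratifies (SAP 1.3), so the lower figures apply.

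The width difference alone can cause disagreement. If both analyses returned the same point estimate and r were 0.4, they would disagree for any observed difference between 0.543 and 0.593 days.

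**Responder endpoints.** At 20% against 31%, the unstratified interval is 0.8% or 1.9% wider than a stratified one if placebo rates vary across strata by ±5 or ±10 points, and 3.9% wider at an extreme ±15. These spreads are assumed. The interval disagrees with the CMH test in 0.2% to 1.0% of trials, so precision is not a material issue there.

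**The case against.** The best reply is that this reads silence as exclusion. The interval sentence in 3.4.1 covers summary tables of counts, changes and percent changes at every interval, for migraine and headache days. The ANCOVA has its own sentence, which does not name even its p-value as an output. The unadjusted reading is therefore an inference about table layout. That is fair, but it remains the natural reading. The parallel rule in 3.4.2 is for two independent proportions and plainly unadjusted, and 3.4.2.4 describes the primary-type output as summary measures plus the p-value.

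Several further points stand:

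- The raw interval is valid, slightly conservative, and matches the displayed arm means. In a linear model it targets the same mean difference.
- Stratified randomisation limits baseline imbalance. In a stratified simulation at r of 0.2 to 0.5, the adjusted and raw estimates differed by only 0.03 to 0.07 day on average.
- The correlation is assumed. At r up to 0.3 the raw interval is at most 5% wider, and the 12.1% figure needs both r = 0.5 and half the planning effect.
- The last repeated-measures model in 2.7.3 adjusts for baseline and uses both missing-data rules, so readers will see an adjusted Weeks 1-12 interval. It omits prophylactic use, though in a simulation where that factor had no prognostic effect, dropping it from the ANCOVA moved the estimate by under 0.001 day.

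These points limit the size of the problem but do not remove it. An interval labelled as sensitivity, from another model, is not the primary estimate.

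**Conclusion.** The concern holds. For the primary analysis the SAP specifies one interval method, and it does not belong to the primary test. Across assumed correlations of 0 to 0.5, the raw interval is 0% to 15% wider than the ANCOVA interval, with coverage of 95.1% to 96.8%. At the planning effect and r of 0.2 to 0.5, the ANCOVA result would be significant beside an interval that includes zero in about 1.0% to 3.7% of trials; the reverse occurs in 0.2% to 0.5%. These figures rest on SD 4, 350 per arm, stratified assignment and the assumed r.

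This is a gap in specification and reporting. It is worth closing because it concerns the trial's headline estimate and costs almost nothing.

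**What to change.** In SAP 3.4.1, add one sentence: the LS-mean difference versus placebo and its 95% confidence interval, from the ANCOVA in section 2.5.1, are the primary estimate and are reported with its p-value. Keep the raw differences and intervals, labelled as descriptive summaries that match the arm means.

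For consistency, a cross-reference in 3.4.2.4 and 3.4.2.5 can ask for the model difference and interval beside the ANCOVA p-values for acute medication days and HIT-6. No precision gain is claimed for these two, because SAP 2.5.2 lists only treatment and the stratification factors as their terms. A Mantel-Haenszel stratum-weighted risk difference with interval in 3.4.2, to match the CMH test, is optional.

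The planned Proc Mixed fit already yields the primary estimate and interval. The change needs no new data and leaves the test, the alpha and the sample size as they are.
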